## RCT

Participants will complete their first visit with research staff at Penn State Hershey, in the Physical Medicine and Rehabilitation Lab in the HCAR building or in the Lime Spring Outpatient Center in Lancaster. These visits are estimated to take 45 minutes. After the baseline visit, research staff will send RCT participants the following questionnaires, via a link to REDCap online: Physical Activity Enjoyment Scale, Depression, Anxiety, Loneliness, International Physical Activity Questionnaire, Lubben Social Network Scale, Sociodemographics, Exercise program preferences, Competitiveness, Tobacco Use, Exercise Self-Efficacy, The Preference for and Tolerance of the Intensity of Exercise Questionnaire (PRETIE-Q), The Affective Exercise Experiences (AFFEXX) and the Perceived Motor Competence Questionnaire for Children (PMC-C). After the baseline visit, research staff will send participants among the Older Adult Feasibility Study the following questionnaires, via a link to REDCap online: Physical Activity Enjoyment Scale, Depression, Anxiety, Loneliness, Sociodemographics, Basic Psychological Needs Satisfaction, and the Perceived Motor Competence Questionnaire for Children (PMC-C). These surveys should take approximately 30 minutes to complete.

Research staff will obtain signature of the informed consent document prior to the in-person visit. Before initiating any research-related activities at the in-person visit, a research staff member will take the individual's blood pressure and heart rate to screen for eligibility and safety. If blood pressure is  $> 160$  systolic OR  $>100$  diastolic OR heart rate is  $> 120$  bpm, research staff will suggest the individual to see a PCP to control their blood pressure or heart rate, and if they would like to still participate in our study they can be tested again in the future. Their PCP will be sent a critical value letter including the blood pressure or heart rate values that were abnormal, and the individual will receive a critical value letter from research staff via mail. Research staff will take the participant's height and weight. Letters will also be provided for critical values on the depression and anxiety measure, as these may be clinically relevant and may warrant an evaluation.

Subjects will complete a maximal test on a treadmill using a single maximal graded treadmill test, using a Bruce protocol and ECG or heart rate monitoring [1] using a metabolic measurement system, such as a COSMED, Parvomedics or other system. Each subject will be hooked up to mask that will collect their expired gases. They will also be connected to the Quinton Q-Stress ECG machine to monitor heart rhythms or they will wear a polar heart rate monitor. Each test will use an incremental exercise test method and subjects will be instructed on how to complete each test. They will also be instructed on how to use the Borg Rated of Perceived Exertion (RPE) scale (6-20). The test will be stopped when  $>2$  mm ST depression are noted on ECG or limited by symptoms. Speed and incline will be adjusted upwards in 3 minute increments consistent with the Bruce protocol.

Samples of gas from each 30-second period will be collected and compared to determine when steady state has been achieved, which is typically in the last 60 seconds of each 3-minute stage. The four criteria that will be used for stopping the test, consistent with when VO2Max has been achieved are 1) plateau in oxygen consumption as workload increases, 2) a respiratory exchange ratio (RER) of greater than 1.05 to 1.15 and 3) a heart rate that is within 10 to 12 beats of the age predicted maximum heart rate (220 - age) or 4) limited by symptoms or > 2mm ST elevation on ECG.

Clinical staff are present to both perform and supervise the individuals, to ensure safety. Testing will be overseen by [name], exercise physiologist and Lab Director.

During this visit, subjects will be provided with explanation about how and when to wear the accelerometer. They will be asked to wear it while awake for 7 days, rather than just when they are active. They will be shown how to wear it, on the waist, so that it captures movement appropriately. Participants will be emailed or called after 48-96 hours to be sure they are wearing it and help troubleshoot in case of difficulty with the monitor.

Research coordinator will provide payment to subjects among the RCT for completing the baseline visit following receipt of the accelerometer.

Household members will not have a baseline visit. Instead, the summary explanation of benefits will be sent to the household member, and they will be given the opportunity to ask questions to study staff. Household members will not be compensated financially.

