##### **7.2.7 Communicating Abnormal Stress Test Results**

In the event of the participant experiencing an elevation of > 2 mm in ST segments on the ECG, [name] will communicate these results by phone with the participant and care provider that

signed the permission form.

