### **10.2 Method of collection of safety information**

Adverse events will be captured by surveys each month, using links to surveys in REDCap. Adverse events that occur during the stress testing will also use the Adverse Event form, which includes details on the outcome of the event as well as the type of injury.

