## 10.7 Suspension of research

As above, the DSMB will review all serious AEs within 2 days and identify an action plan and report that to the sponsor and the IRB within 7 days. The DSMB plan may include stopping the study, either temporarily or permanently.

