## **13.0 Sharing Results with Subjects**

We will communicate any critical values of a clinical measure (e.g., blood pressure, depression and anxiety screen) to subjects.

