#### **16.4 Availability of medical or psychological resources**

In case of emergencies, the PI (a primary care physician) will contact the subject and recommend or refer to appropriate medical or psychological resources.

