## 19.0 Adverse Event Reporting

### 19.1 Reporting Adverse Reactions and Unanticipated Problems to the Responsible IRB

In accordance with applicable policies of The Pennsylvania State University Institutional Review Board (IRB), the investigator will report, to the IRB, any observed or reported harm (adverse event) experienced by a subject or other individual, which in the opinion of the investigator is determined to be (1) unexpected; and (2) probably related to the research procedures. Harms (adverse events) will be submitted to the IRB in accordance with the IRB policies and procedures.

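### Section 7.2.7 requires a call to the care provider only for ST elevation, although 7.2.6 also stops the RCT treadmill test for ST depression

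*Combined protocol and SAP*

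**What the plan says.** Section 7.2.6 (Visit 1, RCT) makes two statements about stopping the maximal treadmill test on ECG grounds. The first stops it when more than 2 "mm ST depression are noted on ECG or limited by symptoms". The second is the last of four stopping criteria in the next paragraph and reads "limited by symptoms or > 2mm ST elevation on ECG". Monitoring is by ECG or, alternatively, by a heart rate monitor.

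Section 7.2.7 (Communicating Abnormal Stress Test Results) specifies a phone call to the participant and to the care provider who signed the permission form. The only trigger it names is an "elevation of > 2 mm in ST segments on the ECG".

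Section 7.2.16 uses the same test protocol at the 6- and 12-month visits.

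**The concern.** The protocol regards ST depression above 2 mm as serious enough to end a test, yet its rule for telling the provider about abnormal results leaves that sign out. Staff who follow 7.2.7 exactly would call about one ST sign and not about the other.

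What is at stake is clinical follow-up. Section 5.2.2 describes the maximal test as the riskiest element of the RCT. Section 11.0 anticipates that an ECG abnormality may later prove false on further testing, but section 7.2 schedules no confirmatory cardiac test, so any such work-up would normally fall to the participant's own provider. The RCT exclusions in 3.2 name no exercise-ECG finding. A participant whose baseline test stopped for ST depression could therefore go on to randomization and sessions up to four times a week without the provider having to be told.

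**Working it through.** No arithmetic applies. The check sets the provisions side by side and then looks for cover elsewhere.

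**Step 1: the three ST statements.**

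| Place | Sign (above 2 mm) | Consequence |
|---|---|---|
| 7.2.6, first stopping statement | ST depression | Test stops |
| 7.2.6, fourth criterion in the next paragraph | ST elevation | Test stops |
| 7.2.7 | ST elevation | Call to participant and provider |

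Elevation has both a stop and a call. Depression has a stop only.

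**Step 2: do the two stopping statements conflict?** No. Staff satisfy both by stopping on either sign. The wording is uneven, but the stop for depression is written.

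**Step 3: does another provision require the call for ST depression?**

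- 7.2.6 sends the primary care provider a critical value letter, but for resting blood pressure or heart rate.
- 13.0: "We will communicate any critical values of a clinical measure (e.g., blood pressure, depression and anxiety screen) to subjects". This might reach the participant. It does not name ECG findings or the provider.
- 16.4: in an emergency the principal investigator "will contact the subject and recommend or refer to appropriate medical or psychological resources". This reaches the participant.
- 10.2: "Adverse events that occur during the stress testing will also use the Adverse Event form". This is a recording rule.
- 10.7: the safety board reviews serious adverse events within 2 days, and must "identify an action plan and report that to the sponsor and the IRB within 7 days". The provider is not a recipient.
- 19.1: "the investigator will report, to the IRB, any observed or reported harm (adverse event) experienced by a subject", limited to harms judged unexpected and probably related. Again the provider is not a recipient.
- 3.3.1 allows the principal investigator to remove a participant who would face unnecessary risk. That is discretion over participation and says nothing about notice.

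Several of these could come into play after a test stopped for ST depression. None obliges anyone to tell the provider.

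**Step 4: how far does the gap reach?**

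- *ECG only.* With a heart rate monitor, no ST change of either kind can be seen.
- *Follow-up tests.* The identical protocol carries the gap forward, but section 7.1 shows that few follow-up tests remain for the cohorts it describes. The 2019 cohort had no 12-month visits and its 6-month visits were cut short. The 2021 cohort's 6-month visits were not feasible. For these cohorts, chiefly the modified 12-month visits of the 2021 cohort are left.
- *Which provider.* Section 7.2.5 has a permission form sent before the baseline visit. Sections 3.2 and 6.2.3, however, tie permission to risk factors, COVID-19 items or screener answers. Some participants may have no provider who signed a form, so a corrected rule needs a fallback.

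**The case against.** The best defence is that this is a drafting slip. The same 2 mm threshold appears three times, the heading of 7.2.7 is general, and the paragraph that names elevation is framed around signs that VO2max has been reached, so it is not a dedicated safety list. The documents do not show which word was intended. That may explain the text, but it does not repair it, because staff act on the written trigger.

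Second, safeguards exist. Clinical staff supervise the test, participants are aged 18 to 50 and screened as low-risk, the principal investigator is a primary care physician, and the safety board includes a cardiologist (10.4). All of this stands and lowers the stakes. None of it is a notification rule.

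Third, the permission form is an attachment that is not in the text available, and consent pages are not available either. Either could say what is reported back to the provider. This also stands, so the claim is limited to the visible protocol text.

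A reader might infer that participants with ST depression have in fact gone unreported, or that the plan means to withhold the result. The documents support neither: they report no ST depression in any test, and staff remain free to call the provider.

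**Conclusion.** The point holds in a narrow form. In the visible protocol text, ST depression above 2 mm stops the RCT maximal test but is not a trigger for the call in 7.2.7, and no other section requires the provider to be told.

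The severity is minor. No endpoint, sample size, power or type I error is involved. The number of affected participants cannot be given, because the documents state neither the share of tests done with ECG nor the frequency of ST depression. A reader might also take 7.2.6 to mean that the test continues through ST depression, since the four-item list omits it. That reading fails, because the preceding paragraph stops the test for it.

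The conclusion rests on two assumptions: that the unseen attachments do not already contain the rule, and that staff apply 7.2.7 as written.

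**What to change.** 1. In 7.2.6, name both ST depression and ST elevation above 2 mm in both stopping statements. The study physician should confirm that both signs are intended.
2. In 7.2.7, make either sign trigger the call to the participant and to the provider who signed the permission form or, where no form was required, to the participant's primary care provider.

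The cost is a wording amendment and a short staff memo. Participants undergo no added procedure. A look back through completed ECG-monitored tests for ST depression that was not passed on is optional and would take limited staff time.

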#### FEASIBILITY STUDIES: Older Adults

Participants will complete their first visit with research staff at Penn State Hershey, in the Physical Medicine and Rehabilitation Lab in the HCAR building. These visits are estimated to take 45 minutes. After the baseline visit, research staff will send participants the following questionnaires, via a link to REDCap online: Physical Activity Enjoyment Scale, Depression, Anxiety, Loneliness, Sociodemographics, Basic Psychological Needs Satisfaction, and the Perceived Motor Competence Questionnaire for Children (PMC-C). These surveys should take approximately 30-minutes to complete.

Research staff will obtain informed consent prior to initiating any research-related activities. Before initiating any research-related activities at the in-person visit, a research staff member will take the individual's blood pressure and heart rate to screen for eligibility and safety. If blood pressure is > 160 systolic OR >100 diastolic OR heart rate is > 120 bpm, research staff will suggest the individual to see a PCP to control their blood pressure or heart rate, and if they would like to still participate in our study they can be tested again in the future. Their PCP will be sent a critical value letter including the blood pressure or heart rate values that were abnormal, and the individual will receive a critical value letter from research staff via mail. Research staff will take the participant's height and weight. Letters will also be provided for critical values on the depression and anxiety measure, as these may be clinically relevant and may warrant an evaluation.

Subjects will complete a Five (5) Times Sit-to-Stand (5TSTS) test, using a standard height chair with a backrest, as a measure to quantify functional lower extremity strength. The 5TSTS test will require study subjects to transfer from a seated to a standing position and back to seated for a total of five (5) times; subjects will be instructed on how to complete the test prior to administration. The test will be stopped when a total of five (5) transfers is achieved, unless limited by symptoms.

Subjects will complete a fourteen (14)-item balance assessment, using a standard height chair

with a backrest as well as a standard height step, as a measure of balance and physical function. The balance assessment will require study subjects to transfer from a seated to a standing position, using several variations of transfer (Berg Balance Scale); subjects will also perform additional, functional balance activities (Berg Balance Scale). Subjects will be instructed on how to complete the test prior to administration. The test will be stopped when completion all fourteen (14) balance items is achieved, unless limited by symptoms.

Subjects will complete a submaximal test using a stepping tool, using an ECG or heart rate monitoring [1] metabolic measurement system, such as a COSMED, Parvomedics or other system. Each subject will be hooked up to mask that will collect their expired gases. They will also be connected to the Quinton Q-Stress ECG machine to monitor heart rhythms or they will wear a polar heart rate monitor. Each test will require the study subjects to step up-and-down a step for a total of 3-minutes; subjects will be instructed on how to complete the test prior to administration. They will also be instructed on how to use the Borg Rated of Perceived Exertion (RPE) scale (6-20). The test will be stopped when a total of 3-minutes is achieved, unless limited by symptoms.

Clinical staff are present to both perform and supervise the individuals, to ensure safety. Testing will be overseen by [name], exercise physiologist and Lab Director.

During this visit, subjects will be provided with explanation about how and when to wear the accelerometer. They will be asked to wear it while awake for 7 days, rather than just when they are active. They will be shown how to wear it, on the waist, so that it captures movement appropriately. Participants will be emailed or called after 48-96 hours to be sure they are wearing it and help troubleshoot in case of difficulty with the monitor.

Research coordinator will provide payment to subjects among the Older Adult Feasibility study for completing the baseline visit following receipt of the accelerometer.

#### FEASIBILITY STUDIES: Adolescent, Major Depression

Prior to the initial in-person visit, participants (and at least one parent in the case of the adolescent feasibility study) will review the consent form via phone call with study staff for 30 minutes. During that time, they will explain the study and complete the informed consent procedures. Of note, potential participants for the Adolescent Feasibility Study will be requested to sign consent upon arrival at the project site, prior to the beginning of any research-related activities. At the initial in-person visit, they will provide an explanation about how and when to wear the accelerometer. After the informed consent procedures are complete, research staff will send participants the following questionnaires, via a link to REDCap online and based on the target population:

Adolescents: Shortened Physical Activity Enjoyment Scale (S-PACES), Basic Psychological Needs Satisfaction, the PROMIS Depression and Anxiety Scale, Brief Loneliness Scale, PMC-C and Sociodemographics.

Adults with Major Depressive Disorder: Physical Activity Enjoyment Scale (PACES), Hamilton Rating Scale for Depression (HAM-D), Sociodemographics, PMC-C, Brief Loneliness Scale, the PMC-C, PSS-10, GAD-7, PHQ-9, WHODAS 2.0, BREQ-3, PESS, EMGI, and the LCE. Of note, the HAM-D will be completed over the phone, by either [name], a clinical psychologist, or a research staff member trained by [name], rather than being completed online.

##### **7.2.7 Communicating Abnormal Stress Test Results**

In the event of the participant experiencing an elevation of > 2 mm in ST segments on the ECG, [name] will communicate these results by phone with the participant and care provider that

signed the permission form.

### **7.2.8 Randomization.**

Once eligible participants who sign the informed consent and completed the baseline questions, research staff at each site will randomize the participant into one of two groups (group fitness, PlayFit) in a one-to-one ratio based on the following stratification factors: age (over and under 35) and gender. The randomization will be performed through REDCap, but participant will not be informed of the group assignment until the accelerometer has been received and the baseline online surveys have been completed. At that point, a project staff member will contact the participant to review the randomization assignment (group fitness, PlayFit) and orient the participant to the program, by explaining how sessions tend to run, what to bring, reviewing possible locations, discussing frequently asked questions and answering any additional question the participant may have. Additionally, the participant will be given the option to install the TeamSnap phone application in order to receive exercise session confirmation and cancellation notifications.

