### 3.3 Early Withdrawal of Subjects

#### 3.3.1 Criteria for removal from study

It is possible we will withdrawal participants from the study if they are unwilling to follow COVID-19-

related safety procedures during the mandate, become injured and cannot exercise or if they are asked by their Primary Care Provider to suspend exercise. The Principal Investigator reserves the right to remove a participant from the study for any reason, based on their discretion, particularly a belief that continued participation exposes them to unnecessary risk. Also, participants have the right to withdraw themselves at any time and halt all study-related activities permanently.

Other withdrawal criteria include: unwillingness to follow exercise protocol during sessions, unwillingness to complete the baseline assessment survey and/or return the accelerometer to study staff, withdrawal of consent by subject, development of a medical problem that would exclude them from the study (e.g., heart disease).

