### **3.3.2 Follow-up for withdrawn subjects**

If the participant contacts us that they want to withdraw from the study, we will ask them to write a note and email it or put it in the mail documenting their desire to withdraw. Once we receive the letter, subjects will be withdrawn immediately. Subjects withdrawn will not have additional intervention or data collection activities schedule. They will not be replaced. For the focus groups, we will replace subjects who are withdrawn.

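### RCT participants can be randomised before the baseline accelerometer is back, so people withdrawn for not returning it become avoidable post-randomisation losses

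*Combined protocol and SAP*

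**What the plan says.** Section 7.2.8 sets two separate triggers. The first is for randomisation: "Once eligible participants who sign the informed consent and completed the baseline questions, research staff at each site will randomize the participant". Device return is not among its conditions. The second is for disclosure: "The randomization will be performed through REDCap, but participant will not be informed of the group assignment until the accelerometer has been received". Completion of the online surveys is a further condition for disclosure. Only then does staff contact the participant to give the assignment and orient them to the programme.

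Section 7.2.6 (RCT) hands out the accelerometer at the baseline visit: "They will be asked to wear it while awake for 7 days". It also sends the online questionnaires after that visit and provides a check on wear: "Participants will be emailed or called after 48-96 hours to be sure they are wearing it and help troubleshoot".

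Section 3.3.1 includes among its withdrawal criteria "unwillingness to complete the baseline assessment survey and/or return the accelerometer to study staff". Section 3.3.2 says of those withdrawn: "Subjects withdrawn will not have additional intervention or data collection activities schedule. They will not be replaced".

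Section 8.3 plans an intent-to-treat comparison of change from baseline to 12 months. It has no rule for people randomised but withdrawn before they learn their arm, and no method for missing outcomes. Section 8.1 allows up to 470 RCT subjects.

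**The concern.** Wearing and returning the device works as a short compliance hurdle: nobody learns an arm or starts sessions until it is cleared. A hurdle of this kind normally stands before randomisation, so that people who fail it are screen failures and do not touch the comparison. Here the allocation may already have been made. A person who will not return the device can then be withdrawn as a randomised participant who was never offered either programme and will have no 12-month VO2max or activity measurement.

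Two things are at stake. The first is information: the intent-to-treat set contains people whose outcome is missing for a reason the trial could have screened out. For activity (MVPA), which Aim 1 names beside VO2max, a person who never returns the baseline device also has no baseline value, so no change score can be formed. The second is protection of the comparison: site research staff run the randomisation, and no section blinds them to the result while devices are still being collected.

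**Working it through.** **Order of events, RCT**

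1. Consent is signed electronically before the baseline visit (4.4, 7.2.6).
2. At the baseline visit the device is handed out for 7 days of wear; the online questionnaires are sent afterwards (7.2.6).
3. Randomisation in REDCap requires consent and completed baseline questions (7.2.8). Device return is not required.
4. Disclosure of the arm requires both the device and the online surveys (7.2.8).

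The text therefore allows a gap between steps 3 and 4 in which a person is randomised but has not returned the device. The withdrawal rule in 3.3.1 can act in that gap.

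**The survey half.** The baseline questions in step 3 are not defined. If they are the online surveys of step 4, survey non-completers are never randomised and only the device is affected. If they are something shorter, both are affected. The documents do not settle this.

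**Size.** The documents give no rate of withdrawal at this step, so the rates below are assumptions.

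- Number lost = rate × 470. At 5%: 0.05 × 470 = 23.5, about 24. At 10%: 0.10 × 470 = 47.
- With randomisation after receipt, the number lost by this route is 0.

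**Power.** Section 8.2 gives a VO2max difference of 2.5 units but no SD, alpha, power or dropout for the RCT, so 470 can be neither reproduced nor refuted. For illustration, take two-sided alpha 0.05, 1:1 allocation and n per arm, with

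power = Φ(2.5 / (SD × √(2/n)) − 1.96).

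Solving for the SD at which 235 per arm gives 80% power: SD = 2.5 / ((1.96 + 0.84) × √(2/235)) ≈ 9.67. A smaller assumed SD of 7 is shown for contrast. The people lost are treated as simply missing, equally in both arms.

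| Assumed loss | People lost | n per arm left | Power, SD 9.67 | Power, SD 7 |
|---|---|---|---|---|
| 0% | 0 | 235 | 80.0% | 97.2% |
| 2% | 9.4 | 230.3 | 79.2% | 96.9% |
| 5% | 23.5 | 223.25 | 78.0% | 96.5% |
| 10% | 47 | 211.5 | 75.8% | 95.7% |
| 20% | 94 | 188 | 70.8% | 93.4% |

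At a 5% to 10% loss the cost is 2.0 to 4.2 percentage points of power at SD 9.67, and 0.7 to 1.5 points at SD 7.

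**The case against.** A reader might go further than the text supports in four ways.

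- **That every late or missing device means a lost randomised participant.** Section 3.3.1 speaks of possible withdrawal and of unwillingness, not of any failure or delay, and 7.2.6 provides contact at 48 to 96 hours to rescue wear. Only those actually withdrawn fall under the no-follow-up rule in 3.3.2. This objection stands.
- **That survey non-completers are certainly lost after randomisation.** As shown above, the wording may already exclude them. This stands; what remains is an undefined term.
- **That the comparison is biased.** Participants do not know their arm, so their own failure to return the device should not depend on it, and arm-independent loss leaves the arms balanced in expectation. No section says that the staff who pursue devices see the allocation or decide removals knowing it. On the other side, site staff perform the randomisation, 9.1.3 gives all project personnel access to the data, and 3.3.1 leaves the investigator wide discretion to remove participants. Influence is therefore not excluded, but nothing shows it.
- **That reordering is free and recovers all these people.** If the cap of 470 is counted at consent, the change turns them into screen failures and adds no analysable participants.

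Timing also limits the remedy. Section 7.1 says the 2019 cohort enrolled from June to December 2019 and the 2021 cohort mainly from June to October 2021, and no later RCT cohort is named. The same section reports that 12-month visits did not occur in the 2019 cohort, which is a larger loss than the one assumed here. This narrows the point to any further enrolment and to reporting. It does not remove it, because the text still permits the sequence and gives no reason for randomising early.

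**Conclusion.** The point holds in limited form. Section 7.2.8 permits randomisation before the accelerometer is received, and possibly before the online surveys are complete. Sections 3.3.1 and 3.3.2 then allow withdrawal at that step without follow-up or replacement. The result is avoidable missing outcomes in an intent-to-treat analysis and some loss of power.

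The size is unknown. About 24 to 47 people rests on an assumed 5% to 10% loss from the full 470, and the power figures rest further on assumed SDs and alpha. A conclusion that staff knowledge of the arm has distorted withdrawals would go beyond the documents. The change is worth making because the plan already treats receipt of the device as the gate for disclosure (7.2.8) and for the baseline payment (7.2.6 and 14.0).

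**What to change.** **For any further RCT enrolment.** Amend 7.2.8 so that the REDCap randomisation is run only after the accelerometer and the completed baseline online surveys have been received, in the same step as the contact that discloses the arm. Replace the undefined reference to baseline questions with the named online surveys. State that, in the RCT, failure to provide the device or the surveys is a pre-randomisation screen failure. Leave 3.3.1 unchanged for the feasibility studies: its list carries no RCT label, and those single-group studies also use accelerometers and baseline surveys.

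**For participants already randomised.** Report by arm the number lost between randomisation and notification, keep them in the intent-to-treat set, and state in 8.3 how their missing 12-month outcomes are handled.

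**Cost.** Wording in 7.2.8, an RCT-specific screen-failure sentence and a line in 8.3, plus a change in the order of one REDCap step. No visit or measurement is added, and participants learn their arm no later than now. The small downside is that, if the cap of 470 is counted at consent, the screen failures use up enrolment without adding analysable participants; the protocol should say at which point the 470 is counted.
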